10.7.4 Urine Drug test

A 5 panel Multi-Line Test will also be conducted at Screening to detect amphetamines, cocaine, THC, opiates and PCP.

10.7.5 Pregnancy Test

Females of childbearing potential only. A serum pregnancy test should be conducted at the Screening visit to assess eligibility using the test kits provided by the central laboratory. A urine pregnancy test will be conducted at Period 1, Day -1 and Period 4 Day 8 following the 24 hrs post dose blood sampling.

Full details of the required sample collection and processing procedures will be described in the study-specific Laboratory Manual.

10.7.6 Breath Alcohol Content Test

Each subject will have a breath alcohol content test at screening and Period 1, Day -1.

10.7.7 COVID-19 Testing

COVID-19 polymerase chain reaction testing (SARS-CoV-2 RT-PCR) of a respiratory specimen (preferably a nasopharyngeal swab) will be performed on Day -2.

10.7.8 ECG

Machine reported standard ECG with overall clinical ECG interpretation will be recorded at Screening in the eCRF.

10.7.9 Overall blood volume

The individual volume of blood collected throughout the study (Screening, PK assessment and Safety Follow up) will be approximately 335.5 ml.

Number of blood samples

Total number of samples per period: 12 PK timepoints, 1 pre-dose and 11 post-dose.

Volume per blood sample

Screening: 15.5 ml

Total blood volume per PK day including 24 hrs post-dose (Period 1, Period 2, Period 3): 78 ml

Total blood volume per PK day including 24 hrs post-dose (Period 4, including safety follow up blood samples): 86 ml

Total blood volume per subject: 335.5 ml

11 SAFETY

11.1 DEFINITIONS

11.1.1 ADVERSE EVENT (AE)

An AE is any untoward medical occurrence in a subject administered a pharmaceutical product and does not necessarily have a causal relationship with this treatment. An AE can therefore be any unfavorable or unintended sign or symptom, intercurrent illness, injury, or any concomitant impairment of the subject's health, temporally associated with the use of a medicinal product, whether or not considered related to the medicinal product.

A treatment-emergent AE is any AE temporally associated with the use of a study drug, whether or not considered related to the study drug.

AEs include:

- Exacerbation of a chronic or intermittent pre-existing condition/disease/symptoms present at baseline that worsen during the study including either an increase in frequency and/or intensity.
- Disease or medical condition detected or diagnosed after study drug administration even though it may have been present prior to the start of the study.
- Events considered by the Investigator to be related to study-mandated procedures.
- Abnormal safety assessments, e.g. laboratory test abnormalities, physical exam findings, ECG or vital sign measurements must be reported as AEs if they represent a clinically significant finding in the medical and scientific judgment of the Investigator, symptomatic or not, which was not present at baseline or if present at baseline, worsened during the course of the study or led to dose reduction, interruption or permanent discontinuation of study drug. However, if an abnormal laboratory or other safety-related test result is associated with clinical signs or symptoms, the signs or symptoms should be recorded as an AE. If signs and symptoms are part of a diagnosis, then the diagnosis should be recorded as AE.
- Signs, symptoms of a suspected drug interaction.
- Signs, symptoms of a suspected overdose of either the study drug or a concomitant medication (overdose per se will not be reported as AE/SAE).

AEs do not include:

- Medical or surgical procedure, e.g., surgery, appendectomy, endoscopy, tooth extraction, transfusion (as these are treatments for an AE). However, the event resulting in the procedure is the AE (e.g. appendicitis, abdominal pain).
- Pre-existing disease or medical condition documented at baseline that does not worsen.

- Situations in which an adverse change did not occur, e.g., hospitalizations for cosmetic elective surgery or for social and/or convenience reasons.
- Anticipated day-to-day fluctuations or seasonal fluctuations (e.g. allergic rhinitis) of pre-existing disease(s) or condition(s) documented at baseline.
- The disease/disorder being studied, or the expected progression, signs or symptoms (including laboratory values) of the disease/disorder being studied, unless it is more severe than expected for the subject's condition.
- Overdose of either study drug or concomitant medication without any signs or symptoms.

11.1.2 SERIOUS ADVERSE EVENT (SAE)

An SAE is any untoward medical occurrence between the time of consent and the subject's final visit that:

- is fatal,
- is life-threatening,
- requires inpatient hospitalization or prolongation of existing hospitalization,
- results in persistent or significant disability/incapacity,
- results in a congenital anomaly/birth defect or
- is otherwise judged as medically significant (may jeopardize the subject).

The following guidelines should be used:

Life-threatening: Refers to an event in which the subject was at risk of death at the time of the event; it does not refer to an event which hypothetically might have caused death if it were more severe.

Inpatient hospitalization: Subject has to stay in hospital at least overnight. The following reasons for hospitalizations are not considered AEs, and therefore not SAEs:

- Hospitalizations for cosmetic elective surgery, social and/or convenience reasons. Standard monitoring of a pre-existing disease or medical condition that did not worsen, e.g., hospitalization for coronary angiography in a subject with stable angina pectoris.
- Elective treatment of a pre-existing disease or medical condition that did not worsen, e.g., hospitalization for chemotherapy for cancer, elective hip replacement for arthritis, vein stripping for preventive and/or cosmetic purpose.

Prolongation of hospitalization: Complications that occur during hospitalization are AEs. However, if a complication prolongs hospitalization or would have required hospitalization or fulfills any other serious criteria, that complication is considered an SAE. In any case, admission to an intensive care unit is considered a prolongation of hospitalization. When in

doubt as to whether “prolongation of hospitalization” was necessary, the AE should be considered serious.

Significant disability: The term significant disability means that there is a substantial disruption of a person’s ability to conduct normal life functions. This definition is not intended to include experiences of relatively minor medical significance such as uncomplicated headache, nausea, vomiting, accidental trauma (e.g. sprained ankle) or uncomplicated chronic diseases which may interfere or prevent everyday life functions but do not constitute a substantial disruption.

Medically significant: Medical and scientific judgment should be exercised in deciding whether other situations should be considered serious such as important medical events that might not be immediately life-threatening or result in death or hospitalization but might/may jeopardize the subject or might/may require intervention to prevent one of the other outcomes listed in the definition above. Examples of such events are invasive or malignant cancers, intensive treatment in an emergency room or at home for allergic bronchospasm, blood dyscrasias or convulsions that do not result in hospitalization, or development of drug dependency or drug abuse.

SAE related to study-mandated procedures: Such SAEs are defined as SAEs that appear to have a reasonable possibility of causal relationship (i.e., a relationship cannot be ruled out) to study-mandated procedures (excluding administration of study drug) such as discontinuation of subject's previous treatment during a washout period, or complication of a mandated invasive procedure (e.g., blood sampling, heart catheterization), or car accident on the way to the hospital for a study visit, etc.

11.2 REPORTING AND DOCUMENTATION

AEs should be documented in terms of a medical diagnosis. When this is not possible, the AE should be documented in terms of signs and/or symptoms observed by the Investigator or reported by the subject at each study visit.

Any pre-existing conditions or signs and/or symptoms present in a subject prior to the start of the study should be recorded on the Medical History CRF.

All SAEs that occur after informed consent is obtained through study completion or premature discontinuation must be reported on the SAE form in the CRF and reported within 24 hours to the Sponsor. All AEs occurring from the time of the first dose of study treatment through study completion or premature discontinuation must be reported on the AE form in the CRF. For AEs related to COVID-19 testing, see section 9.2.

Any SAE that occurs during the clinical study or within two weeks of receiving the last dose of study drug, whether or not related to the study drug, must be reported to the Sponsor.

Deaths or congenital abnormalities if brought to the attention of the Investigator AT ANY TIME after cessation of study drug AND considered by the Investigator to be possibly related to study drug, should be reported to the Sponsor.

At each visit AEs will be solicited. The nature of each event should be established. Details of changes to study drug dosing or any subsequent treatment should be recorded on the appropriate pages of the CRF.

AEs already documented in the CRF (i.e., at a previous assessment) and designated as 'ongoing' should be reviewed at subsequent visits as necessary. Upon resolution, the date of resolution should be recorded in the CRF. If an AE increases in frequency or severity during a study period, a new record of the event should be started. If the AE lessens in intensity, no change in the intensity is required as only the worst intensity must be reported.

All AEs and SAEs, including those that are ongoing at the end of the study or at premature discontinuation, will be followed up until resolution or stabilization or until the event is otherwise explained.

11.2.1 Immediate Reporting

The following AEs must be reported within 24 hours to the Sponsor or designee:

- SAEs
- Pregnancy (not considered as an AE, but must be reported immediately)

For immediate reporting, the Investigator must fill out the SAE form (also for pregnancies) and send to the Sponsor within 24 hours after awareness.

SAFETY CONTACT DETAILS

Primevigilance Limited has been contracted by the Sponsor for safety reporting

Email SAE reports to [contact] or fax to [contact]

Contact details for safety questions will be provided in the Investigator Site File

If the site obtains relevant follow-up information, this information needs to be forwarded to the Sponsor within 24 hrs of awareness using a new SAE form and the updated AE form if appropriate.

Other documents must be submitted upon request. All documents must be blinded with respect to the subject's personal identification to meet data protection requirements, e.g., on the discharge summary this data must be blinded, and the subject number added.

As soon as the Sponsor is informed about an SAE, an evaluation and potential reporting to central IRBs/IECs, Competent Authorities (CA) and other concerned parties will occur as required. The Investigator will be responsible for reporting to any local IRB/IEC as required.

11.2.2 Non-Immediate Reporting

AEs that do not qualify for immediate reporting will be documented in the eCRF and reported in the Clinical Study Report (CSR).

11.3 EVALUATION

AEs and the corresponding entries in the eCRF will be reviewed by the Investigator or qualified member of the study staff. Adverse events, toxicities and medical surgery/history will be categorized by primary system organ class (SOC) and preferred term using the MedDRA dictionary. Toxicities will also be graded as mild, moderate or severe.

11.3.1 Intensity

The intensity will be rated by the Investigator as “mild”, “moderate” or “severe”:

Mild: Symptoms barely noticeable to the subject or does not make the subject uncomfortable; does not influence performance or functioning.

Moderate: Symptoms of a sufficient severity to make the subject uncomfortable; performance of daily activity is influenced; subject is able to continue in study.

Severe: Symptoms cause significant discomfort; incapacitation or significant impact on the subject’s daily life; may cause cessation of study treatment.

A mild, moderate or severe AE may or may not be serious. These terms are used to describe the intensity of a specific event (as in mild, moderate, or severe myocardial infarction). However, a severe event may be of relatively minor medical significance (such as severe headache) and is not necessarily serious. For example, nausea lasting several hours may be rated as severe, but may not meet the definition of seriousness. Fever of 39 °C that is not considered severe may become serious if it prolongs hospitalization.

11.3.2 Causality

The following should be considered when evaluating the relationship of AEs and SAEs to the study treatment:

Not related: There is not a possibility that the event has been caused by the product under investigation. Consideration should be given to factors, including but not limited to, a lack of reasonable temporal relationship between administration of the drug and the event, the presence of a biologically implausible relationship between the product and the AE (e.g. the event occurred before administration of drug), or the presence of a more likely alternative explanation for the AE.

Related: There is a possibility that the event may have been caused by the product under investigation. Consideration should be given to factors, including but not limited to a positive re-challenge, a reasonable temporal sequence between administration of the drug and the event, a known response pattern of the suspected drug, improvement following discontinuation or dose reduction, a biologically plausible relationship between the drug and the AE or a lack of an alternative explanation for the AE.

11.3.3 Outcome

The outcome of each AE has to be assessed as follows:

- Fatal: The AE resulted in death (“Death” is recorded as an outcome, not as the AE)
- Ongoing/Not resolved: The AE has not resolved
- Recovered with sequelae: Resolution of the AE has occurred, but the subject retains some sequelae
- Recovered: The AE fully resolved with no observable residual effects
- Unknown: The outcome of the AE is not known as the subject did not return for follow-up and attempts to locate the subject and/or to obtain follow-up information were unsuccessful (lost to follow-up).

11.4 RE-EXPOSURE

If an AE requires discontinuation of IMP and is judged to be treatment-related by the Investigator or by the Sponsor, re-exposure is not allowed. If an AE requires dose reduction or discontinuation of IMP and is judged by the Investigator or by the Sponsor to be unrelated to investigational products, the decision to re-introduce the medication or to increase the dose of the medication requires prior approval of the Sponsor or designee.

11.5 SAFETY ENDPOINTS

During the study, safety endpoints will be treatment-emergent AEs and SAEs, including clinically significant changes from baseline in vital signs, physical examination and routine clinical laboratory abnormalities.

12 STATISTICAL CONSIDERATIONS

12.1 SAMPLE SIZE AND POWER CALCULATIONS

The sample size is based on the comparisons of each of the primary PK parameters C_{max} and AUC_{last} for total serum iron between the formulations, within each of the two conditions: fed and fasted. Each comparison will be made via the ratio of the two values of the parameter between the formulations. The 90% confidence interval (CI) for this ratio will be reported.

For each of the two comparisons (suspension vs capsule (fed condition); suspension vs capsule (fasted condition)) the CIs for two parameter ratios (C_{max} and AUC_{last}) for serum iron will be calculated, making a total of 4 CIs. If these ratios were all independent, and the probability of being within (80%, 125%) was 80% for each, then the probability that all 4 would fall within the required limits would be $(80\%)^4 = 41\%$. With individual probabilities of 90%, the combined probability would be 66%. However, if the ratios were positively correlated, the combined probabilities would be higher.

Data from a previous study (ST10-01-101) were used to provide estimates of the standard deviations (SDs) of the logs of the within-subject ratios of the parameters C_{max} and AUC_{last} , for both total serum iron and TSAT. Assuming the SD is no greater than 0.38, if the true ratio is 1, 31 subjects would provide a probability of at least 80% of all 4 CIs lying within (80%, 125%).

The aim of the study is to demonstrate that the 4 CIs for serum iron are all within (80%, 125%). As the SD, and the degree of correlation, are uncertain, 32 subjects will be recruited to the study.

12.2 STATISTICAL METHODS

For each of serum iron, maltol, maltol glucuronide, TSAT, TIBC, UIBC and transferrin, concentration data will be listed for each individual subject, by formulation / condition. The concentration data will be summarized, for each formulation / condition, at each time point by using the following descriptive statistics: n (the number of subjects), arithmetic mean, standard deviation (SD), geometric mean, coefficient of variation (CV), median, minimum and maximum, and a 90% confidence interval (CI) for the mean.

Concentration-time courses of each component will be graphically displayed per subject. Plots of the geometric mean and its 90% CI, by formulation, will be provided, overlaid, for each condition separately.

For serum iron, baseline corrected serum iron, maltol, maltol glucuronide, TSAT, TIBC, UIBC and transferrin, PK parameters (C_{max} , T_{max} , AUC_{last} , AUC_{inf} , λ_z , $t_{1/2}$) will be calculated by non-compartmental analysis and listed by subject and by period. The parameters will be summarized, for each formulation / condition, by using the following descriptive statistics: n, arithmetic mean, SD, geometric mean, CV, median, minimum and maximum.

For each analyte, the within-subject ratios between capsule and suspension of C_{max} , AUC_{last} and AUC_{inf} will be also be calculated and listed per subject, for each of the fed and fasted conditions separately. These ratios will be summarized by n, geometric mean and a 90% confidence interval for the mean.

Other endpoints and safety data will be listed and summarized for each formulation.

Full details will be specified in the Analysis Plan prior to database lock.

All secondary endpoints will be summarized by formulation / condition:

1. Treatment-emergent Adverse Events (TEAEs)
2. Serious Adverse Events (SAEs)
3. Treatment-emergent Adverse Events leading to premature discontinuation of study drug/PK assessments
4. Routine clinical laboratory safety blood results
5. Changes in vital signs
6. Concomitant medications

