6.2 SECONDARY OBJECTIVES

To evaluate the pharmacokinetics (PK) after a single 30 mg dose of ferric maltol administered as a capsule or oral suspension (fasted and fed conditions); through measurements of transferrin saturation (TSAT), baseline corrected serum iron, transferrin, total and unsaturated iron binding capacity (TIBC and UIBC), and plasma of maltol and maltol glucuronide.

To assess the safety and tolerability after a single dose of 30 mg Ferric Maltol administered as a capsule or oral suspension (fasted and fed conditions); based on vital signs, adverse events, concomitant medications and routine clinical laboratory safety blood tests.

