10.7 LABORATORY ASSESSMENTS

10.7.1 Hematology and Clinical Chemistry

Routine clinical laboratory safety bloods for hematology (3.0 mL) and clinical chemistry/iron markers (7.5 mL) evaluations will be collected at Screening to assess eligibility. Hematology (3 mL) and clinical chemistry (5.0 mL) will be repeated at Period 4; 24 hrs post-dose sampling or at the Follow-up visit for early discontinued subjects. Additional testing may be required if any abnormal value is reported and this must be followed until it is resolved.

All analyses will be conducted by a central laboratory. Procedures for the collection, processing, storing, and transporting of samples to the laboratory will be fully described in the study-specific Laboratory Manual.

Investigators will review, sign and date all lab results upon receipt from the central laboratory. If a value is flagged as outside of the normal range, the Investigator must document the abnormality as 'clinically significant' (CS) or 'non-clinically significant' (NCS). Any lab abnormality assessed as 'CS' must be recorded as an AE if not explained by a pre-existing condition (documented in the medical history).

The signed paper copy of the laboratory report is retained at the investigational site. The electronic data transferred from the central laboratory database to the clinical study database will be considered source data for the derivation of summary data and listings presented in the clinical study report.

10.7.1.1 *Hematology test parameters*

Red blood cell count, hemoglobin, hematocrit, white blood cell count (total and differential (% and absolute), absolute reticulocyte count and platelet count.

10.7.1.2 *Clinical Chemistry and Screening Iron Markers test parameters*

Clinical Chemistry: ALT, AST, alkaline phosphatase, gamma-glutamyl transpeptidase (GGT), total bilirubin, creatinine, blood urea nitrogen (BUN), sodium, potassium, chloride, calcium, total cholesterol, uric acid, glucose, total protein, albumin, bicarbonate, LDH, CK, triglycerides

Iron Markers: serum iron, transferrin, transferrin saturation (TSAT), total and unsaturated iron binding capacity (TIBC, UIBC).

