3.6.2 Treatment-Emergent Adverse Event

A treatment-emergent adverse event (TEAE) is defined as an AE that emerges, having been absent prior to the study, or an AE that worsens in severity after the first dose of study drug in this study. Each treatment period will be defined as the period from the date and time of study drug dosing up to but not including the date and time of study drug dosing for the next treatment period (or end of study for the last treatment period). TEAEs that started during a treatment period will be attributed to the corresponding treatment. TEAEs will be summarized by MedDRA system organ class (SOC) and preferred term (PT) for each formulation / condition and overall. The number and percentage of subjects experiencing TEAEs, and the number of TEAEs will be tabulated. Subjects reporting more than one adverse event for a given MedDRA preferred term will be counted only once for that term using the most severe incident. Subjects reporting more than one type of event within a system organ class (SOC) will be counted only once for that SOC. The following summaries of adverse events will be presented for each part:

- Overall summary of TEAEs by formulation / condition with a breakdown by AE maximum severity;
- TEAEs by SOC and PT by formulation / condition;

- TEAEs by SOC, PT, and relationship to study drug by formulation / condition;
- TEAEs by SOC, PT, and maximum severity by formulation / condition; and
- TEAEs by SOC, PT, maximum severity, and the relationship to study drug by formulation / condition.

Separate listings will be prepared for SAEs, AEs leading to death and AEs leading to study discontinuation.

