3.6.3 Safety Laboratory

Blood samples for safety laboratory will be collected at Screening and Day 8/ET.

Safety laboratory values and changes from baseline will be summarized at each scheduled visit by treatment sequence. A table summarizing abnormal values of safety laboratory tests will also be presented. All safety laboratory data, including normal ranges and abnormal laboratory flags, will be provided in data listings.

Pregnancy test results, drug and alcohol testing results, hepatitis and HIV test results, and COVID-19 test results will be listed.

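### Haematology and chemistry are sampled only at Screening and after Period 4, so they cannot be summarised by formulation or condition, and laboratory adverse events dated to Day 8 fall to the Period 4 treatment by sequence alone

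*Protocol*

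**What the plan says.** The safety objective in Protocol 6.2 reads "To assess the safety and tolerability after a single dose of 30 mg Ferric Maltol administered as a capsule or oral suspension", fasted and fed, and is "based on vital signs, adverse events, concomitant medications and routine clinical laboratory safety blood tests". Protocol 12.2 says that "All secondary endpoints will be summarized by formulation / condition"; item 4 of the list that follows is routine laboratory safety results. The synopsis makes the same promise for safety data in general.

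Protocol 10.7.1 fixes the sampling: "hematology (3.0 mL) and clinical chemistry/iron markers (7.5 mL) evaluations will be collected at Screening to assess eligibility", after which haematology and chemistry "will be repeated at Period 4; 24 hrs post-dose sampling or at the Follow-up visit for early discontinued subjects". SAP 3.6.3 agrees on timing: "Blood samples for safety laboratory will be collected at Screening and Day 8/ET". It then summarises values and changes from baseline by treatment sequence, not by formulation/condition.

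On adverse events, Protocol 10.7.1 says "Any lab abnormality assessed as 'CS' must be recorded as an AE if not explained by a pre-existing condition". SAP 3.6.2 defines a treatment period as running from one dose to the next, with the last period running to the end of the study, and says "TEAEs that started during a treatment period will be attributed to the corresponding treatment".

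**The concern.** A crossover can describe safety by treatment only if something is measured after each treatment and before the next. Haematology and chemistry are not. The protocol promises a laboratory summary that the sampling cannot support, and the SAP replaces it with a grouping that does not separate the treatments either.

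The attribution rule adds a second problem. If an investigator grades a Day 8 value clinically significant and dates its onset to that draw, the event enters the by-treatment tables under one treatment, although the subject has taken four. A reader of those tables, in a study meant to support interchangeability of capsule and suspension, could take this as evidence about a formulation when it reflects only the sequence.

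**Working it through.** **1. Confirm the sampling from the blood budget (Protocol 10.7.1, 10.7.2, 10.7.3, 10.7.9).**
- Screening: 3.0 + 7.5 + 5 = 15.5 mL.
- PK tubes per period: 12 × (4 + 2.5) = 78 mL.
- Period 4: 78 + 3 + 5 = 86 mL.
- Total: 15.5 + 3 × 78 + 86 = 335.5 mL.

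Each line matches the protocol's own figure. Periods 1 to 3 are used up by PK tubes, so they contain no safety bloods.

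**2. Count exposures with their own safety sample.** Planned exposures are 32 × 4 = 128. Those followed by a safety sample before any further dose number 32, and 32/128 = 25%. All are in Period 4. With dosing on Days 1, 3, 5 and 7, the Day 8 draw comes about 168, 120, 72 and 24 hours after the four doses.

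**3. See what attribution to Period 4 means (sequences in SAP 2.2.1).**

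| Sequence | n | Period 4 treatment |
|---|---|---|
| A | 8 | suspension, fasted |
| B | 8 | capsule, fasted |
| C | 8 | suspension, fed |
| D | 8 | capsule, fed |

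Each treatment in Period 4 comes from exactly one sequence, so treatment and sequence cannot be told apart. A formulation contrast within a food state would be 8 subjects against 8 other subjects, not a within-subject contrast in 32. For a continuous laboratory change with equal variances, the variance ratio is (2/8) ÷ (2(1 − ρ)/32) = 4/(1 − ρ). With an assumed within-subject correlation ρ of 0, 0.5 or 0.8 this is 4, 8 or 20. Even then, every completer has also had the other three treatments.

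**4. Check the baseline.** SAP 3.2 takes the pre-dose reading of each period, or failing that the last reading before first dosing. No safety bloods are scheduled on a dosing day, so the laboratory baseline is the Screening value. The only change available in a completer is Screening to Day 8, across all four doses.

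**5. Blood drawn before or at the Day 8 sample.** PK sampling takes 4 × 78 = 312 mL. The documents give no blood volume. As an illustration only, with an assumed 4 to 5 L and full volume replacement, 312/5000 = 6.2% and 312/4000 = 7.8%. From an assumed haemoglobin of 14 g/dL that is about 0.9 to 1.1 g/dL with no drug effect. Gradual loss and marrow response would make it smaller.

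**The case against.** The strongest reply is that Protocol 12.2 leaves full details to the analysis plan, and the SAP plans no by-formulation laboratory table. On that view only a wording mismatch and a missing pooled column remain. It is true that the SAP does not make the unsupported comparison. But the protocol sentence still stands, SAP 3.6.3 gives no reason for the change, and the by-sequence table is not a useful substitute. The reply also leaves the attribution rule untouched.

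Several stronger readings are tempting, and the documents do not support them:
- *The safety objective cannot be answered.* It rests on several sources together and states no comparative hypothesis. Adverse events and concomitant medications are attributed by period, and vital signs are taken on each PK day. The gap is confined to haematology and chemistry.
- *No laboratory value belongs to one treatment.* Serum iron, TSAT, TIBC, UIBC and transferrin are measured in every period. A subject who stops after Period 1 also gives a single-treatment safety sample.
- *Every laboratory event found on Day 8 goes to Period 4.* The rule follows onset, not detection. An event that the investigator dates earlier goes to the earlier period.
- *The rule biases the comparison.* Period 4 is planned at 8 subjects per treatment, so neither formulation is favoured.
- *A fall in haemoglobin from sampling will appear as a treatment-emergent event.* It does so only if the value is graded clinically significant and entered as an event. The investigator may judge it not related, and the SAP tabulates relationship.

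The number of affected events may also be small or zero. In study ST10-01-103, with 10 days of twice-daily dosing in 37 children and adolescents, no laboratory abnormality was considered treatment-emergent (Protocol 5.4.3). The population differs, but this tempers the practical weight.

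**Conclusion.** The point holds for scheduled haematology and chemistry. The protocol's by-formulation/condition laboratory summary cannot be produced from the planned samples. The SAP's by-sequence summary conflicts with it and does not inform on formulation or food state. A clinically significant abnormality with onset dated at the Day 8 draw is assigned to one of the four treatments received, by sequence alone.

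The sampling and attribution conclusions rest on the documents and assume no statistical parameters. The variance ratios and the haemoglobin figures do depend on assumptions and are illustrations. The consequence is limited to descriptive secondary safety tables: the primary PK analysis, the iron markers and adverse events dated to earlier periods are unaffected. It is worth correcting before database lock, but it does not threaten the study's main conclusion.

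**What to change.** - **Protocol 12.2:** remove item 4 (laboratory results) from the by-formulation/condition list, and reconcile that section and the matching synopsis sentence with SAP 3.6.3.
- **SAP 3.6.3:** summarise the Screening-to-Day 8 change pooled over all subjects as the effect of the whole four-dose study, and state that it is not attributable to a formulation or condition. Say how early-termination samples are handled, since they may follow fewer doses.
- **SAP 3.6.2:** show adverse events first detected from the Day 8 safety bloods in a separate all-treatments row instead of under the Period 4 treatment.
- **Interpretation:** beside the pooled haemoglobin change, note that 312 mL of PK sampling precedes or coincides with the Day 8 draw. Label any estimate of the resulting fall as dependent on an assumed blood volume.

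The cost is wording in both documents, a change to the laboratory table, one extra row in the adverse event tables, and a way to identify events first found in the Day 8 bloods. No new samples are needed. The downside is that no by-formulation laboratory safety statement is made. Obtaining one by repeating the 8 mL draw in Periods 1 to 3 would bring the total to 15.5 + 4 × 86 = 359.5 mL, which is 24 mL above the 335.5 mL ceiling in Protocol 5.6. The reporting change avoids this.
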